12.5. Safety and Tolerability Analyses

The following safety and tolerability measures monitored throughout the study and summarized:

- AEs
- EPS Scales (AIMS, BARS, and ESRS-A)
- Presence of akathisia
- C-SSRS

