Randomization to ARI-ORAL: Patients will continue with ARI-ORAL doses within the recommended oral dosage range for the treatment of schizophrenia (10-30mg/day) with the usual starting dosage of 10 mg/day. ARI-ORAL dosage will be flexible and dosage will be at the discretion of the treating psychiatrist. Patients assigned to this treatment arm will receive a written prescription for a 30-day supply along with a medication coupon so there will be no medication cost to the patient.

Discontinuation of Assigned Treatment

Both groups will remain on their assigned treatment for 12 months or discontinue their assigned medication early. The reason(s) for early discontinuation of initial antipsychotic will be recorded, including whether it is initiated by the clinician or patient, and whether it is efficacy or tolerability related. Patients will be assessed for the reason for discontinuation using a version of the All-Cause Discontinuation (ACD) measure that was the primary outcome of the CATIE schizophrenia study. If a switch to another antipsychotic medication is warranted, the new therapy will be determined by the prescribing psychiatrist's judgment using the medication selection recommendation adapted from NAVIGATE pharmacologic treatment manual developed as part of the Recovery After an Initial Schizophrenia Episode (RAISE) study intervention groups. Patients discontinuing study drug after Randomization, but remaining in active treatment and follow-up, may be prescribed any first-line oral antipsychotic within the prescribing information dosage for schizophrenia. Patients will be encouraged to stay in the study for the remainder of the 12-month Treatment period and will be administered all of the scheduled assessments even if the initial randomly assigned antipsychotic medication is discontinued by the treating psychiatrist.

Symptom assessments will occur every two weeks, functional endpoint will occur every three months, and the cognitive endpoint will occur at baseline and at the 6- and 12-month points. All patients participating in the protocol will be invited to concurrently participate in a separate NIMH-funded psychosocial intervention protocol comparing the effectiveness of computerized cognitive training with and without aerobic exercise training.

Number of Patients Planned: Approximately 128 patients enrolled into the Stabilization period for final randomized sample of 90 (45 in each group) with a target of 14 relapses

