6.3. Discontinuation of Assigned Medication

If the randomly assigned medication must be discontinued and/or switched to a different antipsychotic medication, the patient may remain in the study until the 12-month assessment point. End of Assigned Treatment assessment point measures will be completed as close to and if possible, just prior to, the discontinuation/switch. Decision to switch medication will be recorded on a modified Clinical Antipsychotic Trials of Intervention Effectiveness (CATIE) All-Cause Discontinuation (ACD) assessment completed by the treating psychiatrist (Stroup et al, 2003). The switch to another antipsychotic medication will be guided by clinician judgment using the medication selection recommendation adapted from the oral antipsychotic guidance used in the RAISE study (Kane et al, 2015). The date the new medication is prescribed will be recorded and used in the analyses. Patients who choose to discontinue study medication will be allowed to re-

initiate study medication at any time during the 12-month follow-up. All other regular assessments will be completed throughout the remainder of the 12-month study.

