7.2.2. Initiation of AL-LAI Treatment Arm after Randomization

Initiation of AL-LAI will begin with a one-day initiation regimen (675 mg AL-NCD and 30 mg oral aripiprazole) per prescribing information ([Initio USPI](#)) unless the alternative initiation is selected (see Section 8.3.4.1.2). Dosing of AL-LAI will be flexible based on clinician judgment per prescribing information ([Aristada USPI](#)). The first AL-LAI injection may be administered on the same day as the one-day initiation regimen or up to ten days thereafter. Treatment with AL-LAI can be initiated at a dose of 441 mg, 662 mg or 882 mg administered monthly, 882 mg administered every six weeks or 1064 mg administered every two months. Patients assigned to the AL-LAI treatment arm will return to the clinic for injections during scheduled visits.

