Abbreviations: ACD= Modified Version of the All-Cause Discontinuation; AIMS = Abnormal Involuntary Movement Scale; BARS=Barnes Akathisia Rating Scale; BPRS= Brief Psychiatric Rating Scale; CGI-S= Clinical Global Impressions-Severity; C-SSRS= Columbia Suicide Severity Rating Scale; GASS= Glasgow Antipsychotic Side-effect Scale; EoT= end of study treatment; ESRS-A=Abbreviated Extrapyramidal Symptom Rating Scale; EoAT = end of aripiprazole treatment; GFS: Role=Global Functioning Scale: Role; Hassles= Family Caregiver Medication Administration Hassles Scale; MCCB=MATRICS Consensus Cognitive Battery; MSQ= Medication Satisfaction Questionnaire (Modified); QLS = Quality of Life Scale; PSP= Personal and Social Performance Scale; SAE = Serious Adverse Event; SANS= Scale for the Assessment of Negative Symptoms; SCID-5= Structured Clinical Interview for DSM-5; SUI-Brief=Brief Substance Use Inventory; SUMD-R= Scale to Assess Unawareness of Mental Disorder-Revised; SES= Services Engagement Scale

¹ For all visits other than Screening and Day 1, the visit will be anchored to the previous visit (based on dosing regimen schedule)

² In the event that a visit is missed or skipped, the additional assessments required at the visit should be conducted (via unscheduled assessment) at the patient's next visit

³ EoT= end of study treatment (may include therapies other than aripiprazole, if changed); EoAT = end of aripiprazole treatment

⁴ The Psychiatric and Social History Schedule will be administered to record basic demographic information as well as past work and school history. Assessment⁵ ARI-ORAL will be prescribed with flexible dosing. The first dose should be administered at the UCLA Aftercare Research Program.

⁶ Urine pregnancy testing will be completed for ALL women. At Visit 1 and 14, a serum pregnancy test will be performed. At Visit 1, the pregnancy test should be completed prior to the administration of the first ARI-ORAL dose. A urine pregnancy test will be conducted at mid-study indicated time points.

⁷ Full physical examination at screening; brief physical examination on Day 1; symptom directed physical exams may be performed as needed at the Investigator's discretion.

⁸ Vital signs include blood pressure, heart rate, respiratory rate, and body temperature

⁹ Clinical Lab Tests include biochemistry (including prolactin) and hematology

¹⁰Will be administered at baseline, Month 3, Month 6, Month 9, and Month 12/ET

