12.2. General Statistical Methodology

12.2.1. Intent-to-Treat Population

The Intent-to-treat (ITT) population will include all patients in the AL-LAI group who received at least one dose of AL-LAI, and all patients in the ARI-ORAL antipsychotic medication group who filled at least one prescription of ARI-ORAL after random treatment assignment. This population will be used for efficacy and safety analyses.

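### The safety population leaves out patients given AL-NCD who never receive AL-LAI, and Section 12.5 does not say how events after a switch are attributed

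*Combined protocol and SAP*

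**What the plan says.** Section 12.5 of the combined protocol and SAP is one sentence and a list: "The following safety and tolerability measures monitored throughout the study and summarized", followed by AEs, the three EPS scales, akathisia and the C-SSRS. It names no comparison groups, no time window and no rule for events that start after a change of antipsychotic.

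The population is set in Section 12.2.1. For the injectable arm: "The Intent-to-treat (ITT) population will include all patients in the AL-LAI group who received at least one dose of AL-LAI". The oral arm contributes patients who "filled at least one prescription of ARI-ORAL after random treatment assignment". The section ends: "This population will be used for efficacy and safety analyses". No separate safety population is defined.

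The Synopsis lists AL-NCD as an investigational product in its own right, and Section 4 describes it as a different intramuscular formulation from AL-LAI. Under Section 7.2.2 the one-day regimen is AL-NCD 675 mg with 30 mg oral aripiprazole, and the first AL-LAI injection "may be administered on the same day as the one-day initiation regimen or up to ten days thereafter".

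On switching, the Synopsis says that patients who stop study drug but stay in follow-up "may be prescribed any first-line oral antipsychotic within the prescribing information dosage for schizophrenia". Footnote 3 of Table 2 says that the end-of-treatment assessment "may include therapies other than aripiprazole, if changed". Section 6.3 adds: "The date the new medication is prescribed will be recorded and used in the analyses". It does not say which analyses.

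**The concern.** A safety population should contain everyone exposed to study drug after randomisation. Here entry to the injectable arm depends on the second product in the sequence, so exposure to the first product alone does not count. A patient who reacts badly to AL-NCD is a natural candidate not to go on to AL-LAI, so the omission is likely to be selective. It also falls on one side only, because the oral arm has no separate initiation injection. Tolerability of the two medication groups is an exploratory objective (Section 5.3), and the omission would favour the injectable.

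The second gap is attribution. Patients who stop their assigned drug may take another oral antipsychotic, are encouraged to stay to Month 12 with all scheduled assessments, and may restart study medication (Synopsis; Section 6.3). Without a rule, a reader of the safety tables cannot tell how many of the extrapyramidal, akathisia or AE entries arose on a drug other than the assigned one.

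**Working it through.** The plan states no figure on this point, so there is none to reproduce. The check is a reading of the entry rule, followed by two illustrations of size.

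**1. Who is in the safety population (AL-LAI arm).**

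| Course after randomisation | In the Section 12.2.1 population? | Reaction reaches the summaries? |
|---|---|---|
| AL-NCD and AL-LAI both given, then a reaction | Yes | Yes |
| AL-NCD, reaction, AL-LAI given later | Yes | Nothing excludes it: Section 7.4.12 collects AEs from consent |
| AL-NCD, reaction, AL-LAI never given | No | No |
| Alternative 21-day oral initiation with AL-LAI given (Section 8.3.4.1.2) | Yes | Yes |

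Only the third row is lost.

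**2. Size of that loss (illustration).** Input: 45 patients per arm (Section 6). The number k who react to AL-NCD and never receive AL-LAI is not given, so 1 to 3 is assumed, with the other 45 − k all receiving AL-LAI. The planned rule shows 0/(45 − k); counting everyone injected shows k/45. Intervals are exact (Clopper-Pearson) 95%.

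| k | Under Section 12.2.1 | All given any injection |
|---|---|---|
| 1 | 0/44 = 0% (upper limit 8.0%) | 1/45 = 2.2% (0.1% to 11.8%) |
| 2 | 0/43 = 0% (upper limit 8.2%) | 2/45 = 4.4% (0.5% to 15.1%) |
| 3 | 0/42 = 0% (upper limit 8.4%) | 3/45 = 6.7% (1.4% to 18.3%) |

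**3. Follow-up on another drug (illustration).** The plan gives no switching rate. If a fraction s of an arm switches at month m and stays to Month 12, the share of arm time off the assigned drug is s × (12 − m)/12, out of 45 × 12 = 540 patient-months.

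- s = 10%, m = 9: 4.5 × 3 = 13.5 patient-months, 2.5%.
- s = 20%, m = 6: 9 × 6 = 54 patient-months, 10%.
- s = 40%, m = 3: 18 × 9 = 162 patient-months, 30%.

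For a given s and m these are upper values: some switchers will leave (20% attrition is planned for, Section 12.1.1) and some may restart study drug (Section 6.3).

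**4. What is already collected.** Section 8.2 records the date of each injection. Section 6.3 records the new-medication date and places the End of Assigned Treatment measures close to the switch. An exposure-based table therefore needs no new data.

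**The case against.** The strongest reply has three parts.

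First, the lost group may be very small. The gap is optional: Section 8.3.4.1.3 allows AL-LAI within 60 minutes of AL-NCD. Patients who receive only AL-NCD also stay under SAE reporting (Section 11.3) and the semi-annual committee review (Section 7.4.9.1). This stands. Safety oversight is not affected, and the number may turn out to be zero. The entry rule still gives the wrong denominator and numerator whenever such a patient occurs.

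Second, Section 5.3 asks whether the medication groups differ, and for that question a comparison by randomised group that includes post-switch follow-up is legitimate. This stands too, and it is why the by-arm table should not be displaced. Promoting an exposure-based table to the main one would give up the randomised comparison.

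Third, the schedule already separates end of study treatment from the end-of-assigned-drug assessment. It does, but Section 12.5 does not say which rating is summarised, and the two share one column of Table 2.

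A reader might also infer two stronger things. One is that the plan prescribes tabulation by assigned arm to Month 12 whatever drug is being taken. It does not: Section 12.5 is silent on grouping and window, AE collection runs to the final visit (Table 2 shows a Month 13 follow-up), and Section 6.3 promises some use of the switch date. The other is that any reaction between AL-NCD and the first AL-LAI dose goes uncounted. Row two of the first table shows otherwise.

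**Conclusion.** The point holds in two parts of unequal weight. The firm part is that Section 12.2.1, as written, excludes from the safety summaries a patient exposed to AL-NCD who never receives AL-LAI, and it does so in the injectable arm only. Each such patient who reacts is worth about 2.2 percentage points of a 45-patient arm; how many there will be is unknown.

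The softer part is an omission. Section 12.5 does not define the grouping, the window or the attribution of events after a switch. By-arm tabulation is the likely default, since Section 12.2.1 describes patients by assigned group, but it is an inference. The 2.5% to 30% range of off-drug time rests wholly on assumed switching of 10% to 40% between Months 3 and 9.

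Neither part bears on the primary efficacy comparison, and neither means that safety events go unrecorded. Both affect how the tolerability results can be read, and both can be settled before analysis.

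**What to change.** In Section 12.2.1, define a separate safety population: all randomised patients who received any study drug after randomisation, including AL-NCD or the oral initiation dose.

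In Section 12.5, state that the by-arm safety table is kept, and give its time window. Beside it, add a supplementary table of AEs by the drug being taken at onset, built from the recorded injection dates and new-medication date. Say how patients who restart study medication are handled. Use the End of Assigned Treatment ratings as the last on-drug values for the EPS scales and akathisia.

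If a post-dose risk window is applied, the sponsor should justify it. The 90-day and 30-day periods in Section 7.5.2 are contraception requirements and should not be borrowed for this purpose; being unequal, they would also carry replacement-drug events under the injectable three times as long (90/30 = 3).

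The cost is a few sentences and a few extra tables, with no added visits or patient burden. The limitation is that the drug-at-onset table is not a randomised comparison and should be labelled as such.

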Criteria for Efficacy Evaluation: Primary Endpoint The primary endpoint will be time to first positive symptom exacerbation and/or relapse following a period of absence or relatively low levels of psychotic symptoms based on the expanded 24-item version Brief Psychiatric Rating Scale. Secondary Endpoints Functional assessment: The Role ratings on the Global Functioning Scale (GFS: Role) will serve as the measure of functional outcome. The GFS: ROLE will be administered every three months throughout the 12-month Treatment period. Cognitive assessment: The Overall Composite T-score from the MATRICS Consensus Cognitive Battery (MCCB) will be the overall index of cognitive performance. The MCCB will be administered every six months throughout the 12-month Treatment period. Exploratory Endpoints Endpoints include Quality of Life, negative symptoms, self-reported awareness of having a mental disorder, service engagement, prolactin-related side effects, treatment satisfaction, and family/caregiver medication administration burden. Safety Assessments Extrapyramidal symptoms will be assessed on three scales (Abnormal Involuntary Movement Scale, Barnes Akathisia Rating Scale, and the Extrapyramidal Symptom Rating Scale). Adverse events (including serious and AEs of special interest), and suicidality will be monitored.
Statistical methods: Sample Size Considerations: Ninety first-episode patients will be randomized (1:1) fashion to either AL-LAI or ARI-ORAL, and based on our previous RCT, assume a 20% attrition rate over 12 months. 45 randomized patients (36 completers) in each group provides at least 80% power. Statistical power considerations are based on the effect sizes observed when comparing long-acting injectable risperidone vs oral risperidone (survival analysis for psychotic relapse: 5% relapse in the risperidone long-acting injectable group and 33% relapse in the oral risperidone group). On the basis of hazard function rates of 5.0% (AL-LAI)

and 33% (ARI-ORAL), the study has 87% power ($\alpha=0.05$). On a more conservative basis of hazard function rates of 7.5% (AL-LAI) and 33% (ARI-ORAL), the study has 78% power ($\alpha=0.05$).

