Efficacy will be evaluated based on the Brief Psychiatric Rating Scale (BPRS) scored for symptom exacerbation or relapse following Subotnik et al. ([Subotnik et al, 2015](#)) and Nuechterlein et al. ([Nuechterlein et al, 2006](#)). Because patients will not be withdrawn from the study if relapse criteria are met, there will be no need to score the BPRS for relapse contemporaneously throughout the study. Secondary outcomes will be role functioning and cognition. Exploratory outcomes will be negative symptoms, suicidality, awareness of having a mental disorder, extrapyramidal and prolactin-related side effects, service engagement, treatment satisfaction, and quality of life. Safety assessments will be collected and monitored.

Figure 1: Study Design

^a 1 to 3 months of stabilization on oral aripiprazole.

^b For 2 weeks prior to Randomization, all patients must be on oral aripiprazole

^c Initiation of treatment per Section 7.2.2

Abbreviations: ARI-ORAL: aripiprazole oral; AL-LAI = aripiprazole lauroxil long-acting injectable; ET = End Treatment; EoS = End of Study

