7.4. Study Procedures

7.4.1. Visit and Assessment Schedule

The schedule of assessments is shown in [Table 2](#). For a missed visit, the site should attempt to contact the patient to reschedule.

Table 2: Schedule of Visits and Assessments

	Screening	Stabilization	Treatment Period ¹					Month 13 Follow-up
			Day 1 (Randomization baseline)	Months 1-5 ²	Month 6	Months 7-11	Month 12 EoT/EoAT ³	
Clinical Visit Number	V1		V2	V3, 4,5,6,7	V8	V9,10,11,12,13	V14	V15
Study Drug Administration			Ongoing throughout study					
Psychiatrist Medication Visit	X		Every month throughout study					
Informed Consent	X							
Eligibility Criteria Review	X		X					
Demographics and Medical History ⁴	X							
SCID-5	X							
ARI-ORAL 2-Week Tolerability Assessment ⁵		X						
Pregnancy Testing ⁶	X		X	X (3 months)	X	X (9 months)	X	X
Urine Drug Screen	X		X		X	An additional test if needed for clinical purposes		
Physical Exam ⁷	X							
AE Monitoring			Ongoing throughout study					
Concomitant Medication Review	X		Every month throughout study					
Vital Signs ⁸ , Weight, Waist Circumference	X		Every 3 months throughout study					
Fasting Clinical Lab Tests ⁹	X		X		X		X	
Plasma aripiprazole measurement					X		X	
MCCB			X		X		X	
GFS:Role ¹⁰	X		X	Every 3 months throughout study				
QLS ¹⁰			X		X		X	
SUI-Brief ¹¹	X		X	X	X	X	X	

	Screening	Stabilization	Treatment Period ¹					Month 13 Follow-up
			Day 1 (Randomization baseline)	Months 1-5 ²	Month 6	Months 7-11	Month 12 EoT/EoAT ³	
Clinical Visit Number	V1		V2	V3, 4,5,6,7	V8	V9,10,11,12,13	V14	V15
Modified MSQ			X		X		X	
ESRS	X		X		X		X	X
AIMS	X		X		X		X	X
BARS	X		X	X	X	X	X	X
GASS			X		X		X	
C-SSRS ¹²	X		X	X	X	X	X	X
SES			X		X		X	
CGI-S			X		X		X	
BPRS	X		X	Every 2 weeks throughout study				
MCCB			X		X		X	
SANS			X		X		X	
PSP			X		X		X	
SUMD-R			X		X		X	
Hassles			X		X		X	
ACD			Ongoing throughout study if assigned medications are discontinued					

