7.4.9.4.2. Hematology, Biochemistry, Metabolic, and Prolactin Assessments

Blood and urine samples for laboratory assessments will be collected at the time points specified in [Table 2](#). Specific hematology, biochemistry, metabolic, and prolactin assessments are listed in [Table 4](#). Samples will be collected in accordance with the site’s usual procedures at the UCLA Department of Pathology phlebotomy station on the first floor of the [name] building next door to the Aftercare Research Program, thereby facilitating convenient blood drawing for laboratory tests.

Table 4: Clinical Laboratory Assessments

Hematology	Biochemistry
Hematocrit	Sodium
Hemoglobin	Potassium
Red blood cell count	Glucose
Total and differential (absolute) white blood cell count	Creatinine
Platelets	Total protein
	Blood urea nitrogen
	Albumin
	Total bilirubin
	Alanine transferase
	Aspartate transferase
	Lactic dehydrogenase
	Gamma-glutamyl transferase
	Alkaline phosphatase
	Creatinine phosphokinase
	A1c
	Blood sugar
	Fasting lipid panel
	Prolactin

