11. ASSESSMENT OF SAFETY

11.1. Definition of Adverse Event

An AE is any untoward medical occurrence in a patient or clinical investigation patient who has been administered a pharmaceutical product. The occurrence may or may not have a causal relationship with the investigational treatment, may include any clinical or laboratory change that does not commonly occur in that patient and is considered clinically significant.

Pregnancy is not considered an AE, although a patient will be withdrawn from the study if a pregnancy occurs. The pregnancy, including a partner's pregnancy, must be reported to Alkermes, and additional follow-up may be required.

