12.3. Demographics and Baseline Data

Demographics and baseline characteristics such as gender, age, race, weight, height, and body-mass index will be summarized using descriptive statistics. Medical history will be summarized using the number of observations and percentage of patients reporting each category. Concomitant medications as well as any protocol deviations will be recorded.

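### Weight, waist, glucose/A1c, lipids and serum prolactin are measured through Month 12, but no post-baseline summary or between-arm comparison of them is planned

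*Combined protocol and SAP*

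**What the plan says.** **What is measured.** In Table 2 (Section 7.4.1), the vital-signs row also covers "Weight, Waist Circumference", at Screening and then every three months. Fasting laboratory tests are marked at Screening, Day 1, Month 6 and Month 12. Footnote 9 states that "Clinical Lab Tests include biochemistry (including prolactin) and hematology". Section 7.4.9.4.2 adds that "Specific hematology, biochemistry, metabolic, and prolactin assessments are listed in" Table 4, which includes glucose, A1c, blood sugar, a fasting lipid panel and prolactin.

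**What is analysed.** Section 12.5 reads "The following safety and tolerability measures monitored throughout the study and summarized", followed by AEs, the three extrapyramidal scales, presence of akathisia and the C-SSRS. Section 12.3 says "Demographics and baseline characteristics such as gender, age, race, weight, height, and body-mass index will be summarized using descriptive statistics". Section 12.4 has the exploratory measures analysed in the same way as the secondary ones.

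**What is aimed at.** Section 5.3 makes tolerability, including sexual and prolactin-related side effects, an exploratory objective. Section 7.1 counts among the exploratory outcomes "extrapyramidal and prolactin-related side effects, service engagement, treatment satisfaction, and quality of life". The Synopsis endpoint list includes "self-reported awareness of having a mental disorder, service engagement, prolactin-related side effects, treatment satisfaction".

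**How a laboratory change becomes an AE.** Under Section 11.1 an AE "may include any clinical or laboratory change that does not commonly occur in that patient and is considered clinically significant".

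**The concern.** The protocol collects a standard set of metabolic and prolactin data for a year in both arms and states an interest in comparing tolerability. The analysis sections then never mention these data after baseline. An analyst who follows 12.5 as written would produce no by-arm result for change in weight, waist, glucose, A1c, lipids or prolactin.

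For the metabolic variables, what remains is AE reporting. It depends on someone who knows the treatment arm deciding that a change is clinically significant, with no threshold given. Gradual shifts in a continuous measure are easily missed that way, and the judgement could differ between arms.

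For prolactin, the gap is narrower. There is a named endpoint and a patient-rated side-effect scale, but the direct measurement is not linked to either. If these comparisons are made later without a plan, a reader cannot tell whether they were chosen after the results were seen.

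**Working it through.** This is mainly a coverage check: each measured variable is looked up in every list that could lead to a reported result.

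| Variable | Collected (Tables 2, 4) | 12.5 | 7.4.9.1 and Synopsis safety lists | Exploratory lists (7.4.8, 10.3.1) | 12.3 |
|---|---|---|---|---|---|
| Weight / BMI | Weight: Screening, then every 3 months | no | no | no | baseline only |
| Waist | Screening, then every 3 months | no | no | no | no |
| Glucose, A1c | Screening, Day 1, Months 6 and 12 | no | no | no | no |
| Fasting lipids | same as glucose | no | no | no | no |
| Serum prolactin | same as glucose | no | no | no | no |

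None of the five has a planned post-baseline analysis. The Section 12.4 rule for exploratory measures does not reach them, because they are not listed as exploratory measures.

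**Prolactin.** The Synopsis and Section 7.1 name prolactin-related side effects, but the body lists (7.4.8, 10.3.1) contain no item of that name. The GASS is the evident candidate. It is completed by the patient at Day 1, Month 6 and Month 12 and falls under the Section 12.4 exploratory analysis. The documents do not give its items, and they do not say which instrument or assay serves the prolactin endpoint.

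**Amount of data.** Inputs: 90 randomised, 45 per arm, and 20% attrition over 12 months (Section 12.1.1), so 45 × 0.8 = 36 completers per arm and 72 in total.

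- Laboratory panels at Months 6 and 12: 90 × 2 = 180 if all are followed; 72 × 2 = 144 from completers alone.
- Weight and waist at Months 3, 6, 9 and 12: 90 × 4 = 360, or 72 × 4 = 288.

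**What those data could show.** For a baseline-adjusted difference with 36 per arm, the 95% interval half-width in SD units is 1.96 × √[(2/36)(1 − r²)], where r is the correlation between baseline and Month 12. The documents give no r for these measures, so I assume a range:

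- r = 0.5: 1.96 × √(0.0556 × 0.75) = 0.40 SD
- r = 0.8: 1.96 × √(0.0556 × 0.36) = 0.28 SD
- r = 0.9: 1.96 × √(0.0556 × 0.19) = 0.20 SD

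Intervals of that width would be worth reporting. The finding does not depend on them.

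**Baseline.** The laboratory row has its own Day 1 mark. The weight and waist row does not: it shows Screening and then one cell for every three months, whereas the GFS: Role and BPRS rows mark Day 1 separately. Whether Day 1 weight and waist exist is therefore unclear.

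**The case against.** **The list is not declared closed.** Section 12.5 never says that only these items will be summarised, and laboratory tests sit under the Safety Assessments heading (7.4.9). A reader might infer that the data will go unanalysed. The documents do not show that; they show that no analysis is specified. That is still a gap, because an unplanned safety comparison in an open-label trial is open to selective reporting.

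**Prolactin harm has another route.** A reader might infer that prolactin effects reach the report only when a clinician records an AE. That is wrong: prolactin-related side effects are a named exploratory endpoint, and the GASS has a planned analysis. What stands is that serum prolactin is not tied to that endpoint.

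**Tolerability has other measures.** A reader might also infer that tolerability rests on movement scales, suicidality and AEs alone. The GASS bears on it. So does the Modified MSQ, which asks about side effects, and so does the modified ACD, which records reasons for medication changes; the Synopsis has discontinuations classed as efficacy- or tolerability-related. All three are listed exploratory endpoints. None is described as using the measured weight, waist, laboratory or serum prolactin values.

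**Independent review exists.** A committee of non-investigators reviews safety assessments twice a year (7.4.9.1). That is monitoring, not a reported between-arm result.

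**Large differences may be unlikely.** Both arms deliver aripiprazole (Section 4). This argues against assuming a large between-arm difference, but an interval that excludes one is also useful. It might be tempting to quote a loss of power from AE-only capture. The documents give neither event rates nor capture fractions, so no such figure is supported.

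**Conclusion.** The point holds as an omission in the safety analysis. Five groups of measurements collected through Month 12 (weight, waist, glucose/A1c, fasting lipids and serum prolactin) have no planned post-baseline summary or comparison. For the first four, the only named reporting route is an AE judged clinically significant with the arm known. For serum prolactin, the plan names a related endpoint and a patient-rated scale but does not say that the assay contributes.

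The size is 144 to 180 laboratory panels and 288 to 360 weight and waist visits without a stated analysis, taking the plan's 90 patients and 20% attrition as given. The primary and secondary conclusions are not affected. This is a cheap improvement that should be made before the data are analysed.

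**What to change.** Add a paragraph to Section 12.5, covering data the protocol already calls for:

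1. By arm, change from baseline to Months 6 and 12 in weight, BMI, waist, fasting glucose, A1c, fasting lipids and serum prolactin. Report each between-arm difference with a 95% confidence interval, adjusted for the baseline value and for NIMH exercise-study status, which Section 12.4 already carries as a predictor.
2. By arm, the proportion crossing reporting thresholds that the sponsor fixes in advance. These serve tabulation only and are not rules for managing patients.
3. A statement that these results are descriptive and lie outside the secondary alpha of 0.025.
4. A sentence naming serum prolactin, alongside the GASS, as a measure for the prolactin objective.

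Use Day 1 as baseline for the laboratory values. For weight and waist, the sponsor should confirm whether the every-three-months row in Table 2 includes Day 1. If it does, use Day 1; otherwise use the last value before randomisation. If that is the Screening value, the between-arm comparison remains valid because it precedes randomisation, but within-arm change will also include the Stabilization period and should be labelled so.

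The cost is one paragraph and a few tables, with no new visits, samples or patients. The downside is a few more descriptive comparisons, handled by giving estimates and intervals without claims of significance.
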